APPENDIX 9: LIST OF ABBREVIATIONS

Abbreviation	Definition
AE	adverse event
ALT	alanine aminotransferase
APC	advanced prostate cancer
AST	aspartate aminotransferase
CAP	College of American Pathologists
C_{avgss}	time-averaged steady-state concentration
CBR	clinical benefit rate
CLIA	Clinical Laboratory Improvement Amendment
C_{maxss}	maximum steady-state concentration
C_{minss}	minimum steady-state concentration
COA	clinical outcome assessment
CR	complete response
CRF	case report form
CT	computed tomography
CTCAE	Common Terminology Criteria for Adverse Events
CTLA-4	cytotoxic T-lymphocyte-associated antigen-4
DNA	deoxyribonucleic acid
DRESS	drug reaction with eosinophilia and systemic symptoms
ECG	electrocardiogram
ECOG	Eastern Cooperative Oncology Group
eCRF	electronic case report form
EDC	electronic data collection
FDA	Food and Drug Administration
FFPE	formalin-fixed paraffin-embedded
FT3	free triiodothyronine
FT4	free thyroxine
GBS	Guillain-Barre Syndrome
GCP	Good Clinical Practice
HCC	hepatocellular carcinoma
HIPAA	Health Insurance Portability and Accountability Act
HRT	hormone replacement therapy
IB	Investigator's Brochure
ICF	informed consent form

Abbreviation	Definition
ICH	International Council for Harmonisation
IEC	Independent Ethics Committee
IHC	immunohistochemistry
irAE	immune-related adverse event
IRB	Institutional Review Board
IV	intravenous(ly)
mAb	monoclonal antibody
mCRPC	metastatic castration-resistant prostate cancer
MDACC	MD Anderson Cancer Center
MG	Myasthenia Gravis
mITT	modified Intent-to-Treat
MRI	magnetic resonance imaging
MSI	microsatellite instable
MSS	microsatellite stable
MTD	maximum tolerated dose
NAF	sodium fluoride
NSCLC	non-small cell lung cancer
ORR	objective response rate
OS	overall survival
PBMC	peripheral blood mononuclear cell
PCWG3	Prostate Cancer Clinical Trials Working Group 3
PD	progressive disease
PD-1	programmed cell death-1
PD-L1	programmed cell death ligand-1
PET	positron emission tomography
PFS	progression-free survival
PI	Principal Investigator
PK	pharmacokinetic(s)
PPK	population pharmacokinetic
PR	partial response
PRO	patient-reported outcomes
Q2W	every 2 weeks
Q3W	every 3 weeks
Q4W	every 4 weeks

Abbreviation	Definition
RCC	renal cell carcinoma
RECIST v1.1	Response Evaluation Criteria in Solid Tumors version 1.1
RNA	ribonucleic acid
SAE	serious adverse event
SCCHN	squamous cell carcinoma of the head and neck
SD	stable disease
SOA	Schedule of Activities
T.bili	total bilirubin
TC-99m	technetium-99m
TOX	trial-limiting toxicity
TRAE(s)	treatment-related adverse event(s)
TSH	thyroid stimulating hormone
ULN	upper limit of normal
USPI	US Prescribing Information
WOCBP	woman of childbearing potential

A prospective study with larger sample size is warranted to confirm that the percentage of tumoral CD8 cells at the time of treatment can determine responsiveness to anti-PD-1 therapy and whether combination therapy can convert tumors from CD8 low to CD8 high. We propose a prospective clinical study in which patients with varying advanced solid tumors will be assigned to 1 of 2 treatment arms based on the percentage of tumoral CD8 cells at the time of treatment. Participants who have a tumor with $\geq 15\%$ CD8 cells (classified as CD8 high) will receive nivolumab monotherapy, and participants who have a tumor with $< 15\%$ CD8 cells (classified as CD8 low) will receive ipilimumab in combination with nivolumab.

It is well recognized that immune infiltration varies across tumor types, and different tumor types may display a range of therapeutic sensitivities. Several ongoing studies are evaluating nivolumab treatment in various tumor types (BMS Nivolumab Studies). To better assess the feasibility of using percent of tumoral CD8 cells as a biomarker for selecting checkpoint inhibitor therapy and to gain more insight regarding the design of the trial, we examined CD8 cells in a set of 195 tumor samples from 10 different tumor types (Figure 7). For tumor types in which anti-PD-1 treatment has been approved, the classification of CD8 high tumor is consistent with the clinical benefit reported. The 15% cutoff was selected based on data from retrospective

## 2 INTRODUCTION

The aim of this study is to provide a prospective classification of CD8 high (immunologically “hot”) versus CD8 low (immunologically “cold”) tumors at the time of treatment, based on the percentage of CD8 cells in a tumor biopsy, and to address the predictive value of the CD8 biomarker for selecting patients for treatment with nivolumab with or without ipilimumab.

The purpose of this document is to provide details of the planned clinical analyses for PICI0025. The analyses specified in this document supersede the high-level analysis plan described in the protocol. Statistical analyses will be performed consistent with the principles of the [ICH Guidance for Industry E9 Statistical Principles for Clinical Trials](#).

## 3 STUDY DESIGN

This is an open-label, exploratory study to evaluate nivolumab with or without ipilimumab, with treatment assigned based on the percentage of tumoral CD8 cells at the time of treatment in participants with varying advanced solid tumors.

After consenting to participate in this clinical trial, participants will undergo a tumor biopsy. The tumor tissue will be sent to a Clinical Laboratory Improvement Amendment (CLIA)- and College of American Pathologists (CAP)-certified Immunohistochemistry and Image Analysis Laboratory to determine the percentage of tumoral CD8 cells. Participants will be assigned an immunotherapy regimen according to the percentage of CD8 cells in their tumor biopsies.

There are two distinct cohorts enrolled in this study.

- **Advanced Metastatic Cancer**: enrolled participants with varying advanced solid tumors.
  - Participants with  $\geq 15\%$  CD8 cells in their tumor biopsies (ie, CD8 high tumors) will be treated with nivolumab 360 mg every 3 weeks (Q3W) for 4 cycles, followed by nivolumab maintenance 480 mg every 4 weeks (Q4W). At the time of disease progression, participants may crossover to the CD8 low arm or discontinue treatment.
  - Participants with  $< 15\%$  CD8 cells in their tumor biopsies (ie, CD8 low tumors) will be treated with nivolumab 360 mg Q3W and ipilimumab 1 mg/kg Q3W for 2 doses and then every 6 weeks (Q6W) for 2 doses, followed by nivolumab maintenance 480 mg Q4W.
- **Advanced Prostate Cancer (Protocol Amendment 3)**: enrolled participants with advanced prostate cancer.
  - Participants with  $\geq 15\%$  CD8 cells in their tumor biopsies will be treated with nivolumab 360 mg Q3W for 4 cycles, followed by nivolumab maintenance

480 mg Q4W. At the time of disease progression, participants may crossover to the advanced prostate cohort CD8 low arm of ipilimumab 3 mg/kg and nivolumab 1 mg/kg or discontinue treatment.

- Participants with < 15% CD8 cells in their tumor biopsies (ie, CD8 low tumors) will be randomly allocated into 1 of 2 treatment arms using different doses of ipilimumab.
  - Prostate Cohort A: nivolumab 1 mg/kg Q3W and ipilimumab 3 mg/kg Q6W for 2 cycles, then nivolumab maintenance 480 mg Q4W until disease progression or intolerable toxicity.
  - Prostate Cohort B: nivolumab 1 mg/kg Q3W and ipilimumab 5 mg/kg Q6W for 2 cycles, then nivolumab maintenance 480 mg Q4W until disease progression or intolerable toxicity.

Up to 200 participants with advanced metastatic cancer could be enrolled. A total of 20 participants with advanced prostate cancer and tumoral CD8 < 15% could be enrolled into the Advanced Prostate Cancer portion of the study (10 per treatment arm).

### 3.1 Protocol Synopsis

The Protocol Synopsis is included in Section 8.1.

### 3.2 Study Objectives and Endpoints

The study objectives and endpoints are listed in Table 1.

**Table 1: Objectives and Corresponding Endpoints**

| Objectives                                                                                                                                                                                                                                                                                                                                                                                                                               | Endpoints                                                                                                                                                                                                                                                                                              |
|------------------------------------------------------------------------------------------------------------------------------------------------------------------------------------------------------------------------------------------------------------------------------------------------------------------------------------------------------------------------------------------------------------------------------------------|--------------------------------------------------------------------------------------------------------------------------------------------------------------------------------------------------------------------------------------------------------------------------------------------------------|
| Primary                                                                                                                                                                                                                                                                                                                                                                                                                           |                                                                                                                                                                                                                                                                                                        |
| 
 
• To determine the clinical benefit rate (CBR) of nivolumab with or without ipilimumab in participants with advanced metastatic cancer, including advanced prostate cancer.
 
• To assess the proportion of participants in the nivolumab plus ipilimumab arm whose tumors will change from CD8 low to CD8 high as measured by a change in the percentage of tumoral CD8 cells.
 
 | 
 
• CBR is the proportion of participants who show clinical benefit, defined as CR, PR, or SD for <math>\geq 6</math> months as best response by RECIST v1.1.
 
• Change in the percentage of CD8 cells in on-treatment biopsies from baseline.
 
 |
| Secondary                                                                                                                                                                                                                                                                                                                                                                                                                         |                                                                                                                                                                                                                                                                                                        |
| 
 
• To determine the safety and tolerability of nivolumab with or without ipilimumab in participants with advanced metastatic cancer, including advanced prostate cancer.
 
                                                                                                                                                                                                                | 
 
• Incidence and severity of AEs based on CTCAE v5.0.
 
• ORR: Defined as CR or PR as best response by RECIST v1.1 assessment.
 
                                                                                                                 |

| Objectives                                                                                                                                                                                                                                                                                                                                                                                                                                                    | Endpoints                                                                                                                                                                                                                                                                                                                                                                                                                                                                                                                                                                                                                                                                                                                                                                                                                                                                                                                                                                                                                                                                                                                                                                                                                                                                                                                                                                                                                                                                                                                                                        |
|---------------------------------------------------------------------------------------------------------------------------------------------------------------------------------------------------------------------------------------------------------------------------------------------------------------------------------------------------------------------------------------------------------------------------------------------------------------|------------------------------------------------------------------------------------------------------------------------------------------------------------------------------------------------------------------------------------------------------------------------------------------------------------------------------------------------------------------------------------------------------------------------------------------------------------------------------------------------------------------------------------------------------------------------------------------------------------------------------------------------------------------------------------------------------------------------------------------------------------------------------------------------------------------------------------------------------------------------------------------------------------------------------------------------------------------------------------------------------------------------------------------------------------------------------------------------------------------------------------------------------------------------------------------------------------------------------------------------------------------------------------------------------------------------------------------------------------------------------------------------------------------------------------------------------------------------------------------------------------------------------------------------------------------|
| 
 
• To determine the ORR of nivolumab with or without ipilimumab in participants with advanced metastatic cancer, including advanced prostate cancer.
 
• To assess the association of percentage of CD8 infiltration in tumor samples with clinical outcomes (ORR, PFS, and OS).
 
                                                                                                                      | 
 
• PFS: Defined as the time from initiation of study therapy to date of first documented progression of disease or date of death due to any cause.
 
• OS: Defined as the time from initiation of study therapy until death due to any cause.
 
                                                                                                                                                                                                                                                                                                                                                                                                                                                                                                                                                                                                                                                                                                                                                                                                                                                                                                                                                                                                                                                                                                                                                                                                                                                            |
| Exploratory                                                                                                                                                                                                                                                                                                                                                                                                                                                   |                                                                                                                                                                                                                                                                                                                                                                                                                                                                                                                                                                                                                                                                                                                                                                                                                                                                                                                                                                                                                                                                                                                                                                                                                                                                                                                                                                                                                                                                                                                                                                  |
| 
 
• To evaluate tumor immune biomarkers and their association with treatment outcomes.
 
• To evaluate changes in prostate-specific antigen (PSA) (advanced prostate cancer).
 
• To assess feasibility of implementing the ApricityCare™ digital application (app) for participants being treated with immune checkpoint inhibitor(s) and the use by study staff of ApricityOncology™ website.
 
 | 
 
• Clinical responses based on a composite biomarker derived from nucleic acids, epigenetics, protein, immune cell characteristics, or other factors (CD8 and other biomarkers).
 
• Additional biomarkers of primary resistance to nivolumab or ipilimumab combined with nivolumab beyond the percentage of tumoral CD8 cells based on additional immune evaluation of baseline and on-treatment biopsies or blood samples.
 
• Potential relationship of T-cell phenotypic characteristics and immune characteristics in the tumor microenvironment in participants on nivolumab monotherapy and nivolumab in combination with ipilimumab with clinical outcomes (clinical benefit endpoints and AEs with an interest in immune-related AEs).
 
• Within each study intervention arm, explore the potential relationship of clinical response/resistance/AE with:                         
 
○ mRNA quantity and expression in tumor and/or PBMCs
 
○ Germline DNA and/or tumor genomics
 
○ Multiparameter cytometry of tumor and/or PBMCs
 
○ Immune markers in PBMCs
 
○ Blood circulating analytes
 
○ TCR repertoire in tumor and peripheral blood
 
○ Baseline and on-treatment microbiome
 
 
 
• Identify molecular (genomic, metabolic, and/or proteomic) biomarkers that may be indicative of clinical response/resistance, safety, pharmacodynamic activity, and/or mechanism of
 
 |

| Objectives | Endpoints                                                                                                                                                                                                                                                                                                         |
|------------|-------------------------------------------------------------------------------------------------------------------------------------------------------------------------------------------------------------------------------------------------------------------------------------------------------------------|
|            | action of nivolumab and/or ipilimumab in combination with nivolumab. 
 
• Change in PSA from baseline (advanced prostate cancer).
 
• Frequency of ApricityCare™ app usage by participants and frequency of ApricityOncology website access by study staff.
 
 |

### 3.3 Determination of Sample Size

A total of up to approximately 200 participants with varying tumor types will be enrolled. Enrollment to initial biopsy may be about 10% higher (ie, approximately 220 participants) to account for unexpected challenges obtaining CD8 infiltration information. The selection of 200 participants allows minimum reasonable numbers in the CD8 high and CD8 low tumor groups in larger tumor populations to report subgroup response rates, the transformation from CD8 low to high, as well as to predict response from marker and clinical information. Details of the sample size determination can be found in the protocol section 9.1.

### 3.4 Analysis Timing

Analysis for the Advanced Metastatic Cancer and Advanced Prostate Cancer portions will be performed independently and at different times due to differences in enrollment timelines.

The analysis of complete data for the clinical study report (CSR), described in the main body of this document, will be performed after all participants have been followed for at least 9 months or have discontinued early from the study, and all data from the study through the clinical cutoff date have been entered and reviewed for completeness.

Analysis of efficacy and safety endpoint may be performed prior to the CSR analysis. These results may be presented and/or published prior to the CSR analysis.

The study will formally end once all participants have either completed the safety and survival follow-up periods or have discontinued early from the study, all data from the study are entered in the clinical database, and the clinical database is locked.

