#### 5.4.1 Primary Efficacy Endpoints

The co-primary endpoint of CBR will be reported among all participants within each study intervention group with a 95% credible interval assuming a beta (0.4, 1.6) prior. CBR is the proportion of participants who show clinical benefit, defined as CR, PR, or SD for  $\geq 6$  months as best response by RECIST v1.1 (Eisenhauer, 2009). Per RECIST, to be assigned a best overall response of complete response (CR) or partial response (PR), changes in tumor measurements must be confirmed by a repeat assessment that should be performed no less than 4 weeks after the criteria for response are first met. The duration of SD is defined as the time from the date of first dose of study intervention until the date of radiographic disease progression per RECIST. If no radiographic progression has occurred and the most recent tumor assessment with overall response of SD occurred  $< 6$  months after the date of first dose of study intervention, the participant will not have met the SD duration criterion and will not

be considered a CBR responder. Participants who do not have a disease assessment will be counted as not having clinical benefit.

For the second co-primary endpoint, the absolute change in the percentage of CD8 cells in on-treatment biopsies from baseline will be reported with a 95% credible interval with no prior for participants in the on-treatment biopsy population. In addition, the number of participants with baseline percentage of CD8 counts < 15% who “convert” from a cold to hot tumor (any on-treatment biopsy with percentage of CD8 counts  $\geq$  15%) will be summarized. The proportion of participants who convert from cold to hot will be reported with a 95% credible interval with no prior.

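### The SAP allows the co-primary CBR to be published before participants can qualify through stable disease, and its SD sentence, read literally, ranks a late unconfirmed PR below SD

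*SAP*

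**What the plan says.** SAP 3.4 states that the CSR analysis "will be performed after all participants have been followed for at least 9 months or have discontinued early from the study". The next paragraph relaxes this: "Analysis of efficacy and safety endpoint may be performed prior to the CSR analysis", and "These results may be presented and/or published prior to the CSR analysis". It names no minimum follow-up, excludes no endpoint and asks for no statement of immaturity.

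SAP 5.4.1 defines the co-primary endpoint: "CBR will be reported among all participants within each study intervention group with a 95% credible interval assuming a beta (0.4, 1.6) prior". Benefit is a best response of CR, PR, or SD of at least 6 months. A CR or PR "must be confirmed by a repeat assessment that should be performed no less than 4 weeks after" the response criteria are first met. For SD, "The duration of SD is defined as the time from the date of first dose of study intervention until the date of radiographic disease progression". For a participant who has not progressed, the rule is: "If no radiographic progression has occurred and the most recent tumor assessment with overall response of SD occurred" less than 6 months after first dose, "the participant will not have met the SD duration criterion and will not" be counted as a responder. The SAP does not say how an unconfirmed CR or PR is treated under the SD duration criterion.

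Protocol 9.3.1.2 uses a different rule for futility monitoring only. There, SD between 12 weeks and 6 months counts as success, and no confirmation of response is needed.

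**The concern.** The 5.4.1 rule is reasonable once everyone still followed has had the chance of a scan at or after 6 months. Before that, ongoing SD in a recent entrant counts as failure, and a recent first response cannot yet be confirmed. Both kinds of participant stay in the denominator, so immaturity can only push the CBR down. PFS and OS censor such participants (SAP 5.4.2.2 and 5.4.2.3), but CBR has no equivalent. The first public figure for a co-primary endpoint could therefore be low by an amount set by the timing of the report and not by the drugs.

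The second problem is in the SD sentence itself. It looks only at the last scan labelled SD. A participant whose tumor shrinks enough to be called PR at the first scan after 6 months, with no confirming scan yet, has a last SD label before 6 months. Read literally, the better tumor result gets the worse score.

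**Working it through.** **The plan's own figures.** Protocol 9.1 assumes a CBR of 20% with a beta(0.4, 1.6) prior. For 32/160 the posterior is Beta(0.4 + 32, 1.6 + 128), with a 95% interval of 14.2% to 26.5%. For 8/40 it is 9.5% to 33.2%. Both match the protocol.

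**When SD can first be credited.** Scan days are counted from Protocol Tables 1 to 4. I take 6 months as 182.6 days and 9 months as 273.9 days (39.1 weeks).

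| Schedule | Scan weeks | Last scan before 6 months (+7 days) | First scan that can credit ongoing SD | Next scan |
|---|---|---|---|---|
| Monotherapy (Tables 1, 3) | 9, 16, 24, 32, 40 | day 168 (175) | day 224, 7.4 months | day 280, 9.2 months |
| Metastatic combination (Table 2) | 9, 15, 23, 31, 39 | day 161 (168) | day 217, 7.1 months | day 273, 8.97 months |
| Prostate combination (Table 4) | 9, 17, 25, 33, 41 | day 175 (182) | day 231, 7.6 months | day 287, 9.4 months |

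Even at the end of its window, no scheduled scan before weeks 31 to 33 reaches 182.6 days. The prostate combination scan comes within a day, so a shorter day count for 6 months would let a late scan there qualify. In Table 2 the even-cycle footnote gives weeks 22 and 30 instead of 23 and 31, which does not change the conclusion.

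**Size of the early bias.** Let A be the months of uniform accrual, t the months from last enrolment to analysis, and s the share of benefit that comes only from SD. The share followed at least m months is (A + t − m)/A, limited to the range 0 to 1. With s = 0.5, SD credit from 7.1 months and confirmed response from 3.9 months (week 17):

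Expected CBR = 10% × (A + t − 3.9)/A + 10% × (A + t − 7.1)/A

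- t = 0, A = 18: 10% × 14.1/18 + 10% × 10.9/18 = 7.8% + 6.1% = 13.9%
- t = 0, A = 24: 8.4% + 7.0% = 15.4%
- t = 0, A = 36: 8.9% + 8.0% = 16.9%
- t = 3: 17.2%, 17.9% and 18.6% for A = 18, 24 and 36

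A second calculation counts only the SD loss: 20% × (1 − s × f), with f = (7.4 − t)/A. Over s = 0.25 to 0.75 and A = 12 to 24 months it gives 10.8% to 18.5% at t = 0, 18.2% to 19.7% at t = 6, and no loss from t = 7.4. For scale, s = 0.5 and f = 0.5 give 15.0%, or 24/160, with an interval of 10.0% to 20.9%.

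**The SD label.** Compare three monotherapy participants, each with SD through week 24 (5.5 months):

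- SD again at week 32: the last SD scan is at 7.4 months, so this counts as benefit.
- PD at week 32: SD duration runs to the PD date, 7.4 months, so on that definition this counts as benefit.
- First PR at week 32, unconfirmed at cutoff: the last SD scan is at 5.5 months, so read literally this counts as no benefit.

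The next scan is at week 40 for monotherapy and week 41 for the prostate combination, both after the 39.1-week CSR minimum. In the metastatic combination arm it is at week 39, which is borderline.

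**The case against.** **SAP 5.4.1 may not govern early reports.** SAP 3.4 says the main body of the SAP describes the CSR analysis. Applying 5.4.1 to an early report is therefore an inference. That is fair, but the SAP offers no other CBR definition for such a report, so either this rule applies or the method is unspecified. Early reporting is also optional, so the bias is possible, not certain.

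**The decisions that matter are protected.** This stands for the SD loss. The first qualifying scan falls inside the 9-month CSR minimum, and futility monitoring has its own rule. The study is also exploratory, without hypothesis testing (SAP 5.4), and the bias runs in the conservative direction.

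**The unconfirmed PR is an ambiguity, not an error.** The SAP does not forbid classing an unconfirmed PR as SD. A participant whose PR is later confirmed is a responder, and one who later progresses has an SD duration beyond 6 months. Only those with neither event by the cutoff are affected, so the number is small. The ambiguity still bears on a co-primary endpoint and is easily removed.

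**Stronger readings that the documents do not support.** A reader might infer that everyone without an SD-labelled scan at 6 months is scored as no benefit. That is wrong, because a confirmed CR or PR counts at any time, and SD followed by PD after 6 months also counts. A reader might also infer that tumor types enrolled late must look worst. The documents give no accrual by tumor type, and Amendment 2 limited enrollment partly on immunotherapy responsiveness, so the ordering cannot be predicted.

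**Conclusion.** The concern holds in two limited parts.

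First, CBR may be published before the CSR with no maturity condition, under a rule that can only understate it until about 7.1 to 7.6 months after first dose. The direction follows from the documents. The size does not, because neither the accrual pattern nor the SD share of benefit is given. The fall from 20% to about 14% to 17% assumes half of benefit is SD, uniform accrual over 18 to 36 months and analysis at the end of accrual. It includes responses not yet confirmable. The loss shrinks quickly as follow-up lengthens.

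Second, on its literal wording the SD sentence scores a late, still unconfirmed PR below continued SD. This concerns few participants and I put no number on it, but it is not confined to early reports.

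The SAP should be changed on both parts. Neither undermines the CSR result as a whole.

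**What to change.** 1. **SAP 3.4.** Limit any pre-CSR report of CBR to participants first dosed long enough before the cutoff to have had a scheduled scan at or after 6 months. Include all of them, early failures as well, so that selection is by first-dose date and not by outcome. The time needed is about 33 weeks plus the 7-day window (231 + 7 = 238 days, or 34 weeks). Nine months is a simple, conservative choice. ORR does not use the SD rule, so an early ORR needs only enough follow-up for a confirmed response, or a statement of the follow-up achieved.

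2. **SAP 5.4.1.** In the sentence on participants without progression, let the most recent assessment qualify when its overall response is SD or better, including an unconfirmed CR or PR.

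The cost is two sentences and a smaller denominator in early CBR reports. No data collection changes.
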